Key Exclusion criteria	
 
• Mixed Plasmodium infections as per light microscopy results
 
• Signs and symptoms of severe malaria according to the World Health Organization (WHO 2015)
 
• Patients with concurrent febrile illnesses (e.g., typhoid fever, known or suspected COVID19)
 
• Repeated vomiting (defined as more than 3 times in the 24 hours prior to inclusion in the study) or severe diarrhea (defined as more than 3 watery stools in the 24 hours prior to inclusion in the study)
 
• Clinically relevant abnormalities of electrolyte balance which require correction, e.g., hypokalemia, hypocalcemia or hypomagnesemia
 
• Anemia (hemoglobin level < 7 g/dL)
 
• Patients of child bearing potential, defined as all girls post first menarche (except for Run-in Cohort)
 
• Pregnant or nursing (lactating) patients
 
• Any surgical or medical condition which might significantly alter the absorption, distribution, metabolism, or excretion of drugs (e.g., HIV patients on ART therapy or TB patients on treatment), or which may jeopardize the patient in case of participation in the study. The investigator should make this determination in consideration of the patient's medical history and/or clinical or laboratory evidence of any of the following: 
 
• Aspartate aminotransferase (AST)/alanine aminotransferase (ALT) > 3 x the upper limit of normal range (ULN), regardless of the level of total bilirubin
 
• AST/ALT > 1.5 and <math>\leq 2 \times</math> ULN and total bilirubin is > ULN
 
• Total bilirubin > 2 x ULN regardless of the level of AST/ALT
 
 
 
• Patients with prior antimalarial therapy or antibiotics with antimalarial activity within minimum of their five (5) plasma half-lives (or within 4 weeks of screening if half-life is unknown)
 
• History or family history of long QT syndrome or sudden cardiac death, or any other clinical condition known to prolong the QTc interval, such as history of symptomatic cardiac arrhythmias, clinically relevant bradycardia or severe heart disease.
 

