## 5.2 Exclusion criteria

Patients meeting **any** of the following criteria are **not** eligible for inclusion in this study. No additional exclusions may be applied by the investigator, in order to ensure that the study population will be representative of all eligible patients.

1. Mixed *Plasmodium* infections as per light microscopy results
2. Signs and symptoms of severe malaria according to [WHO 2015](#) (see [Section 16.4](#))
3. Significant, non-plasmodial co-infections including tuberculosis
4. Patients with concurrent febrile illnesses (e.g., typhoid fever, known or suspected COVID19)
5. Known relevant liver disease e.g. chronic hepatitis, cirrhosis, compensated or decompensated, history of hepatitis B or C, hepatitis B or A vaccination in last 3 months, known gallbladder or bile duct disease, acute or chronic pancreatitis
6. Major congenital defects
7. Any confirmed or suspected immunosuppressive or immunodeficient condition, including human immunodeficiency virus (HIV) infection or family history of congenital or hereditary immunodeficiency
8. Immunosuppressive therapy (steroids, immune modulators or immune suppressors) within 3 months prior to recruitment. (For corticosteroids, this will mean prednisone, or equivalent,  $\geq 0.5$  mg/kg/day. Inhaled and topical steroids are allowed)
9. Repeated vomiting (defined as more than 3 times in the 24 hours prior to inclusion in the study) or severe diarrhea (defined as more than 3 watery stools in the 24 hours prior to inclusion in the study)
10. Active duodenal ulcer, ulcerative colitis, Crohn's disease, chronic (i.e.,  $> 2$  weeks) use of non-steroidal anti-inflammatory drugs (NSAIDs)
11. Clinically relevant abnormalities of electrolyte balance which require correction, e.g., hypokalemia, hypocalcemia or hypomagnesemia
12. Anemia (hemoglobin level  $< 7$  g/dL)
13. Any surgical or medical condition which might significantly alter the absorption, distribution, metabolism, or excretion of drugs (e.g., HIV patients on ART therapy or TB patients on treatment), or which may jeopardize the patient in case of participation in the

study. The investigator should make this determination in consideration of the patient's medical history and/or clinical or laboratory evidence of any of the following:

- $AST/ALT > 3 \times$  the upper limit of normal range (ULN), regardless of the level of total bilirubin
  - $AST/ALT > 1.5$  and  $\leq 2 \times$  ULN and total bilirubin is  $> ULN$

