  - Total bilirubin  $> 2 \times$  ULN regardless of the level of AST/ALT
14. Resting QT interval corrected by Fridericia's formula (QTcF)  $> 450$  ms at screening
  15. Creatinine  $> 2 \times$  ULN in the absence of dehydration. In case of dehydration, creatinine should be  $< 2 \times$  ULN after oral/parenteral rehydration
  16. Any severe disease condition which might prohibit participation in this study
  17. Known chronic underlying disease such as sickle cell disease, and severe cardiac, renal, or hepatic impairment
  18. Known active or uncontrolled thyroid disease
  19. Inability to swallow oral medication (in tablet and/or liquid form)
  20. Patients with prior antimalarial therapy or antibiotics with antimalarial activity within minimum of their five (5) plasma half-lives (or within 4 weeks of screening if half-life is unknown)
  21. Use of other investigational drugs within 30 days of dosing or until the expected pharmacodynamic effect has returned to baseline, whichever is longer
  22. Patients taking medications prohibited by the protocol
  23. Previous participation in any malaria vaccine study or received malaria vaccine in any other circumstance within 3 months of dosing
  24. History or family history of long QT syndrome or sudden cardiac death, or any other clinical condition known to prolong the QTc interval, such as history of symptomatic cardiac arrhythmias, clinically relevant bradycardia or severe heart disease
  25. Use of agents known to prolong the QT interval unless it can be permanently discontinued for the duration of study
  26. History of hypersensitivity to any of the study drugs or its excipients or to drugs of similar chemical classes

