## 10.2 Additional Safety Monitoring

### 10.2.1 Liver safety monitoring

To ensure patient safety and enhance reliability in determining the hepatotoxic potential of an investigational drug, a standardized process for identification, monitoring and evaluation of liver events has to be followed.

The following two categories of abnormalities / adverse events have to be considered during the course of the study (irrespective of whether classified/reported as AE/SAE):

- Liver laboratory triggers, which will require repeated assessments of the abnormal laboratory parameter
- Liver events, which will require close observation, follow-up monitoring and contributing factors are recorded on the appropriate CRFs and reported as SAEs.

Please refer to [Table 16-2](#) in [Appendix 2](#) for complete definitions of liver laboratory triggers and liver events.

Every liver event defined in [Section 16.2](#), should be followed up by the investigator or designated personnel at the trial site, as summarized below. Additional details on actions required in case of liver events are outlined in [Table 16-3](#).

- Repeat liver chemistry tests (i.e. ALT, AST, total bilirubin (TBL), PT/INR, ALP and GGT) to confirm elevation.
- These liver chemistry repeats should be performed using the local laboratory used by the site. Repeated laboratory test results must be reported as appropriate.
- If the initial elevation is confirmed, close observation of the patient will be initiated, including consideration of treatment interruption if deemed appropriate.
- Discontinuation of the investigational drug (refer to the Discontinuation of study treatment section), if appropriate
- Hospitalization of the patient if appropriate
- Causality assessment of the liver event
- Thorough follow-up of the liver event should be done. The follow-up should be based on investigator's discretion and can include: serology tests, imaging and pathology assessments, hepatologist's consultancy; obtaining more detailed history of symptoms and prior or concurrent diseases, history of concomitant drug use, exclusion of underlying liver disease

All follow-up information and procedures performed must be recorded as appropriate in the CRF.

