## 16.2 Appendix 2: Liver event and Laboratory trigger Definitions and Follow-up Requirements

**Table 16-2 Liver event and laboratory trigger definitions**

	Definition/ threshold
Liver laboratory triggers	
 
3 x ULN < ALT / AST ≤ 5 x ULN
 
1.5 x ULN < TBL ≤ 2 x ULN
 

Liver events	
 
ALT or AST > 5 x ULN
 
ALP > 2 x ULN (in the absence of known bone pathology)
 
TBL > 2 x ULN (in the absence of known Gilbert syndrome)
 
ALT or AST > 3 x ULN and INR > 1.5
 
Potential Hy's Law cases (defined as ALT or AST > 3 x ULN and TBL > 2 x ULN [mainly conjugated fraction] without notable increase in ALP to > 2 x ULN)
 
Any clinical event of jaundice (or equivalent term)
 
ALT or AST > 3 x ULN accompanied by (general) malaise, fatigue, abdominal pain, nausea, or vomiting, or rash with eosinophilia
 
Any adverse event potentially indicative of a liver toxicity*
 

*These events cover the following: Hepatic failure, fibrosis and cirrhosis, and other liver damage-related conditions; the non-infectious hepatitis; the benign, malignant and unspecified liver neoplasms TBL: total bilirubin; ULN: upper limit of normal
	

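### Exclusion criterion 13: with bilirubin above 1 and up to 2 x ULN, AST/ALT above 1.5 and up to 2 x ULN is listed as evidence for exclusion, but the worse range above 2 and up to 3 x ULN is not

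*Protocol*

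**What the plan says.** Criterion 13 in Protocol Section 5.2 excludes children with a surgical or medical condition that might significantly alter drug disposition, or that could put the child at risk by taking part. On how to decide, it says: "The investigator should make this determination in consideration of the patient's medical history and/or clinical or laboratory evidence of any of the following". Three limits follow:

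1. AST/ALT above 3 times "the upper limit of normal range (ULN), regardless of the level of total bilirubin".
2. The combined line: "AST/ALT > 1.5 and \leq 2 \times ULN and total bilirubin is > ULN".
3. "Total bilirubin > 2 x ULN regardless of the level of AST/ALT".

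The Protocol summary (Key Exclusion criteria) and Section 5.2 carry the same three limits, with the same upper bound of 2 x ULN in the combined line. No other exclusion criterion sets a numerical AST/ALT or bilirubin limit. Criteria 5, 16 and 17 cover known relevant liver disease, severe disease and severe hepatic impairment.

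For the period after entry, Table 16-2 (Section 16.2) names "1.5 x ULN < TBL ≤ 2 x ULN" as a liver laboratory trigger. Section 10.2.1 describes such triggers as: "Liver laboratory triggers, which will require repeated assessments of the abnormal laboratory parameter".

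**The concern.** A list of safety limits should not name a milder profile and pass over a worse one. This list does so when bilirubin is above normal but not above 2 x ULN. A child with AST/ALT at 2.0 x ULN is named. A child with the same bilirubin and AST/ALT at 2.5 x ULN is not.

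Two things are at stake: the safety of children as young as 6 months, and consistent eligibility across the sites of a multicentre trial. Section 5.2 opens by telling investigators not to add exclusions of their own. One site could therefore read the upper bound of 2 x ULN as deliberate and enrol the child, while another excludes the same child on general risk grounds. The upper corner of the unlisted range, for example AST/ALT 2.9 with bilirubin 1.9 x ULN, lies just below both laboratory thresholds of the protocol's potential Hy's Law definition (AST or ALT above 3 x ULN and bilirubin above 2 x ULN).

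**Working it through.** There is no planned figure to reproduce. The check is whether the three limits, taken together, are ordered.

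**Inputs.** The three limits in Section 5.2 no. 13. Let A be AST/ALT and B total bilirubin, both in multiples of ULN. A is treated as one value, since the protocol writes the two enzymes together.

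**Rule as written.** A pair is listed if A > 3, or (1.5 < A ≤ 2 and B > 1), or B > 2.

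| AST/ALT (x ULN) | Bilirubin 1.0 | Bilirubin 1.6 | Bilirubin 2.1 |
|---|---|---|---|
| 1.5 | no | no | listed |
| 1.6 | no | listed | listed |
| 2.0 | no | listed | listed |
| 2.1 | no | **no** | listed |
| 2.5 | no | **no** | listed |
| 2.9 | no | **no** | listed |
| 3.0 | no | **no** | listed |
| 3.1 | listed | listed | listed |

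At bilirubin 1.0 the status changes once, above 3 x ULN. At 2.1 every value is listed. Only the middle column reverses. The pattern is the same for any B above 1 and up to 2, because B enters the combined line only through B > 1 and the third limit only through B > 2. The gap is therefore 2 < A ≤ 3 with 1 < B ≤ 2.

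**Overlap with the protocol's own trigger.** Table 16-2 sets the bilirubin trigger at above 1.5 and up to 2 x ULN. The part of the gap with 1.5 < B ≤ 2 meets it. The part with 1 < B ≤ 1.5 does not. AST/ALT in the gap meets no transaminase trigger, since that starts above 3 x ULN.

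**Rule with the combined line extended to 3 x ULN.** A pair is listed if A > 3, or (1.5 < A ≤ 3 and B > 1), or B > 2. This reduces to:

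- B ≤ 1: listed when A > 3
- 1 < B ≤ 2: listed when A > 1.5
- B > 2: always listed

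Each band now has a single threshold, and the threshold falls as bilirubin rises, so no reversal is possible. On a 0.01-step grid (A from 0 to 5, B from 0 to 3), the pairs whose status changes run from A = 2.01 to 3.00 and B = 1.01 to 2.00. That is the gap and nothing else.

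**Counts on a coarse grid.** Take A in {1.0, 1.5, 1.6, 2.0, 2.1, 2.5, 2.9, 3.0, 3.1} and B in {1.0, 1.1, 1.5, 1.6, 1.9, 2.0, 2.1}, giving 9 x 7 = 63 pairs. Count a reversal for each listed pair matched with an unlisted pair at least as high on both values.

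- As written: 2 listed A values x 4 unlisted A values x 15 ordered combinations of the 5 bilirubin values = 120 reversals.
- Combined line to 3 x ULN: 0 reversals, 4 x 5 = 20 pairs newly listed, all in the gap.
- Stand-alone AST/ALT limit lowered to above 2 x ULN instead: 0 reversals, 4 x 6 = 24 pairs newly listed, namely the same 20 plus 4 with bilirubin at 1.0 x ULN.

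These counts show the logic only. They say nothing about how many children are affected.

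**The case against.** The strongest reply is that the three lines are not cut-offs. They are evidence for a judgement, so a listed child is not automatically excluded and an unlisted one is not automatically admitted. The risk clause is part of criterion 13, so using it is not an added exclusion of the kind Section 5.2 forbids. This stands, and it limits the practical effect. It does not explain why the evidence list should name 2.0 x ULN and omit 2.5 x ULN at the same bilirubin.

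A second reply is that the range is mild by the protocol's own thresholds. It lies below the potential Hy's Law definition and below the laboratory-only AST/ALT and bilirubin thresholds for liver events. The Table 16-2 trigger applies during the study, not at entry, and covers only part of the gap. For an asymptomatic patient in that part, Table 16-3 asks for a repeat test within a week and close observation if the elevation is confirmed. All of this is correct. Yet the still milder range just below the gap is listed, so mildness cannot be the reason for the omission.

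A third reply points to other safeguards. Jaundice counts as a sign of severe malaria (Section 16.4), which criterion 2 excludes. Patients stay in hospital until Day 4. Clinical chemistry is scheduled at 24 h, 48 h and Days 8, 29 and 43, although footnote 13 to Tables 8-2 and 8-3 allows fewer draws in Cohorts 1 and 2. These lessen the consequence of enrolling such a child. They do not make the entry limits coherent.

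Finally, the documents do not state the intended bound, so the clinical team should confirm it.

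**Conclusion.** The concern holds. The listed limits are out of order for AST/ALT above 2 and up to 3 x ULN with bilirubin above 1 and up to 2 x ULN, and nowhere else. The same bound stands in the Protocol summary and in Section 5.2, so this is not a slip in one place or a text-extraction error. It is an inconsistency in a paediatric safety criterion, softened but not cured by investigator judgement.

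The number of children in this range cannot be derived from the documents. Sample size and the primary analysis do not depend on the point. The conclusion assumes only that a higher AST/ALT at the same bilirubin is no less a reason for exclusion.

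**What to change.** In the Protocol summary and in Section 5.2 no. 13, change the upper bound of the combined line from 2 to 3 x ULN, so that it reads: AST/ALT above 1.5 and up to 3 x ULN with total bilirubin above ULN.

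Lowering the stand-alone AST/ALT limit to above 2 x ULN would also close the gap. It is a wider change, because it would also list children with normal bilirubin and AST/ALT above 2 and up to 3 x ULN.

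The cost is one bound changed in two places in a protocol amendment, and possibly some additional screen failures. Sample size and the primary analysis stay as they are. The SAP's revision history refers to a dry run for the study report, so enrolment may already be complete. In that case, identify the children who were in this range at baseline when interpreting liver events, and correct the wording before the criterion is reused.

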## 1 Introduction

### 1.1 Background

Malaria caused by *Plasmodium falciparum* is one of the leading causes of death in the developing world.

In 2018, an estimated 228 million cases of malaria and 405,000 deaths occurred worldwide: 93% of malaria cases and 94% of malaria deaths were in the African Region; and about half of all malaria deaths came from six countries (Nigeria, Democratic Republic of the Congo, Tanzania, Angola, Mozambique and Niger) (WHO 2019). Children aged under 5 years are the most vulnerable group affected by malaria, which accounted for 67% (272 000) of all malaria deaths worldwide in 2018 (WHO 2019).

Malaria is caused by *Plasmodium* parasites. There are five parasite species that cause malaria in humans, and two of these species – *P. falciparum* and *P. vivax* – pose the greatest threat. *P. falciparum* is the most prevalent malaria parasite on the African continent. It is responsible for most malaria-related deaths globally. *P. vivax* is the dominant malaria parasite in most countries outside of sub-Saharan Africa.

Standard antimalarial drugs such as chloroquine (CQ), pyrimethamine (PYR), sulfadoxine (SFDX) and mefloquine (MEF) have become largely ineffective in many malaria endemic regions. The only exceptions are the artemisinin-based combination therapies (ACTs) such as Novartis' Coartem®/Riamet® and Eurartesim®, current standard-of-care for *P. falciparum* malaria. Unfortunately, some recent reports (Ashley et al 2014, Ménard et al 2016) suggest that decades of continuous use of artemisinin and bisquinoline derivatives as monotherapies may have fostered the emergence of drug resistance in *Plasmodium* species in Southeast Asia. Reduced *in vitro* susceptibility of *P. falciparum* to artemisinin in this region has been documented (Dondorp et al 2009). Recent studies showed that artemisinin resistance extends over more of Southeast Asia than had previously been known, and is now present close to the border with India (Conrad and Rosenthal 2019, Ménard et al 2016). If widespread artemisinin drug resistance was to occur, malaria pharmacotherapy would be severely impaired. This finding signifies that spread of resistance is inevitable, thus there is urgent need for new antimalarials with new mechanisms of actions.

In addition, current *falciparum* malaria treatments require at least a 3-day dosing regimen which may contribute to therapeutic non-compliance in some patients. Indeed, patients often have resolution of clinical symptoms within 1 to 2 days and may neglect taking final doses. This may contribute to the development of drug resistance.

There is therefore a strong medical need for new chemical entities with a new mode of action as additional treatment options for this very common disease with substantial morbidity and mortality. Simplifying regimens by developing treatments that can be used in a once daily dose for possibly less than 3-day administration can improve treatment success and reduce probability of developing resistance via improved adherence and thus accelerate malaria eradication.

KAF156 (Ganaplacide) is the first drug from a different and novel class of drugs called imidazolepiperazines and was developed by the Novartis Institute for Tropical Diseases (NITD)

following a high through-put screening (HTS) of the Novartis compound library by the Genomics Institute of the Novartis Research Foundation (GNF). KAF156 is structurally distinct from currently marketed antimalarial drugs and other experimental antimalarial compound classes in development. The mechanism of action of KAF156 is still being characterized, but may be related to a previously uncharacterized gene (*P. falciparum* cyclic amine resistance locus, Pfcarl). KAF156 kills/inhibits the erythrocytic replication life cycle stages (blood stages) of the two main causative agents of human malaria, *P. falciparum* and *P. vivax*, both at low nanomolar EC50s (*in vitro*). In addition, KAF156 has shown activity in liver stage models of *Plasmodium* infection, conferring causal prophylactic protection in animal infection models. Limited evidence of gametocytocidal activity may confer transmission blocking activity. KAF156 has not demonstrated activity against liver hypnozoites and therefore has a low probability to be used for a radical cure of *P. vivax* infections. Also, KAF156 is equally potent against drug-sensitive and a broad panel of drug resistant malaria strains (Kuhlen et al 2014; Koller et al 2018).

KAF156, when combined in a fixed-dose formulation with an anti-malarial partner drug, could offer a much needed new treatment for malaria, including in areas where resistance to ACTs is emerging. A fixed-dose formulation with a single-dose regimen to ensure patient adherence to the full treatment would be an ideal option. However, the development of such single-dose regimens is more challenging in terms of maintaining adequate blood levels during 6-7 days (3 parasite replication cycles). Considering the impending risk of resistance to existing antimalarials and higher risk of therapeutic failure with a single day regimen, a two day or a three day regimen will be evaluated (based on the outcomes of the run-in cohort).

[figure not shown]
Lumefantrine-Solid Dispersion Formulation (LUM-SDF) will be used as partner drug in this study. In contrast to the conventional lumefantrine formulation, LUM-SDF has an improved bioavailability and less food effect, leading to an exposure which allows for a potentially curative once daily two-day regimen. KAF156 does not have a food effect. KAF156 and LUM-SDF in combination were assessed in a Phase 2b dose finding study (CKAF156A2202, Part A). Outcomes of the interim assessment in acute malaria patients of 12 years and older under fasted condition showed that all doses were efficacious, safe and well tolerated.

## 1.2 Purpose

This Phase 2 study aims to evaluate the efficacy, safety and tolerability of the investigational drug KAF156 and a Solid Dispersion Formulation of lumefantrine (LUM-SDF) when administered in combination once daily in pediatric patients 6 months to < 18 years of age with uncomplicated *Plasmodium falciparum* malaria. After completion of the Run-in cohort in patients 12 to <18 years, a reference product Coartem® will be used as comparator in patients 6 months to <12 years of age. In addition, pharmacokinetics (PK) of the drug combination will also be evaluated.

There will be three age-descending cohorts: Run-in Cohort (12 years to < 18 years), Cohort 1 (2 years to < 12 years) and Cohort 2 (6 months to < 2 years).

It is important to understand the impact of food on exposure. In adult healthy volunteers, LUM-SDF alone has shown a food effect whereas KAF156 does not have a food effect. This new study will first explore the effect of food on lumefantrine and KAF156 PK in malaria patients

12 to < 18 years old with malaria caused by *P. falciparum*. Based on the data from the Run-in Cohort, recommendation on dose, dosing regimen, dosage administration (with food) and duration will be provided before younger patients in Cohorts 1 and 2 are dosed with KAF156/LUM-SDF.

Then, efficacy, safety, tolerability and PK of the combination of KAF156/LUM-SDF in comparison with Coartem® will be evaluated in younger patients, in Cohort 1 of patients 2 to < 12 years old and Cohort 2 of patients 6 months to < 2 years old.

